Multicenter double-blind placebo-controlled randomized parallel group clinical study of efficacy and safety of MMH-MAP in the treatment of cognitive disorders in patients with ischemic stroke in the carotid arteries

Phase III

Sponsor

OOO «NPF «MATERIA MEDICA HOLDING»

Protocol number Version date:

ClinicalTrials.gov Id:

MMH-MAP-002 June 11, 2019 NCT04295681

Protocol Summary

This document represents the protocol summary for the study on human subjects. The study will be carried out in accordance with ICH GCP, National Standard of the Russian Federation GOST 52379-2005 "Good Clinical Practice", World Medical Association Declaration of Helsinki, relevant requirements of the regulatory authorities as well as the study procedures.

Title of Study

Multicenter double-blind placebo-controlled randomized parallel group clinical study of efficacy and safety of MMH-MAP in the treatment of cognitive disorders in patients with ischemic stroke in the carotid arteries.

Phase: III

Sponsor: Company «MATERIA MEDICA HOLDING», Moscow, Russia *Protocol No.* MMH-MAP-002

Purposes of the study

- To evaluate efficacy of MMH-MAP in the treatment of cognitive disorders in patients with ischemic stroke in the carotid arteries.
- To evaluate the safety of MMH-MAP in the treatment of cognitive disorders in patients with ischemic stroke in the carotid arteries.

Endpoints

Primary endpoint

1. Average MoCA score on treatment day 90.

Secondary endpoints

- 1. Changes in NIHSS score on treatment day 12, 90.
- 2. Percentage of patients with no major disability (mRs 0-1) after 90-day therapy.
- 3. Therapeutic and adverse effects, efficacy index according to clinical global impression scale (CGI-EI) after 90-day therapy.

Safety assessment

- Percentage of patients with sequelae of cerebral infarction (severe infections hospitalacquired pneumonia, uroinfection; deep venous thrombosis, PATE; epileptic episodes) during IMP therapy.
- Frequency of all-cause mortality outcomes during IMP therapy.
- Percentage of patients with recurring cerebral infarction during IMP therapy.
- Occurrence and nature of adverse events (AEs) during the treatment, their intensity (severity), relation to the study drug, outcome.

- Changes in vital signs during IMP therapy.
- Percentage of patients with clinically relevant abnormal laboratory tests during IMP therapy.

Study design

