Medical history	+			
Concomitant conditions and diseases	+			

Physical examination	+	+		+
Evaluation of vital				
signs (HR, RR, BP) ***	+	+		+
Recording therapy for				
concomitant diseases	+	+	+	+
Filling MoCA scale	+			+
Filling Glasgow scale	+			
Filling NIHSS scale	+	+		+
Filling mRs scale	+			+
Pregnancy test	+			
Safety laboratory tests	+			+
Inclusion/exclusion	+			
criteria				
Randomization	+			
Dispensing of study	+	+		
drug				
Study drug				
accountability and		+		+
return				
Treatment compliance		+		+
Evaluation of study	Ŧ	Ŧ	Т	–
treatment safety	т	Ŧ	Ŧ	т
Filling CGI-EI scale				+
Visit completion	+	+	+	+
Study completion				+

* The end of the inpatient period is the last day of hospitalization for the current stroke

** Study completion

**** HR - heart rate; RR - respiration rate; BP - blood pressure

Statistical Analyses

Samples

Total set includes all the subjects who have signed ICF. This sample will consider all adverse events (AEs) throughout the study, including those occurred prior to the study therapy.

The sample including all patients who received at least one dose of the study drug to be used for *analysis of the study treatment safety and tolerability* (*Safety population*), as all AEs identified after the study drug administration will be recorded.

Full Analysis Set This sample will consist of all enrolled patients, except for those who met at least one of the following criteria:

- 1) non-compliance with inclusion/exclusion criteria;
- 2) patient did not take any dose of study drug;
- 3) absence of any patient data after administration of study drug.

This was the best set for the Intention-to-treat method, so it will be used in the Intention-to-treat

efficacy analysis (ITT-analysis) of the study therapy.

Per Protocol set. This sample includes all patients who received full protocol therapy and completed all scheduled visits. This set will be used for *Per Protocol analysis (PP analysis) of efficacy of study therapy. Per Protocol set* will not include the patients whose data are fully or partially invalid for analysis due to a protocol deviation.

Protocol deviations resulting in full or partial data invalidity:

- 1. Violation of visit schedule.
- 2. Inappropriate distribution/issue of the study drug.
- 3. Prescription of prohibited therapy.
- 4. Increase or decrease of 25% or more in the amount of study therapy received.

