where N_T – terminal sample size; N_{PP} – result of calculation in c. 1.7 i.e. scheduled number of patients completing the study per protocol; K_B – withdrawal rate.

2. Assumptions on expected clinical study effects.

It is assumed that the difference between the changes in the mean total MoCA score in the Study Drug and Placebo groups on Day 90 of treatment will be at least 1.3 points with a standard deviation of at least 3.0 points.

Therefore, group size needed to compare Study Drug and Placebo will be **98** patients for each group. Given potential withdrawal of at least 20% patients ($K_B = 0.2$) during the study for various reasons, at least **246** patients will be required to sign informed consent, with **123** patients per group (see cl. 1.8).

Statistical criteria

All statistical calculations will be made using two groups of statistical criteria:

- parametric to obtain effective estimates for random parameters in case the relevant conditions of method/model applicability are not violated (e.g. sphericity, normality, risk proportionality, etc.)
- nonparametric in all other cases.

Parametric criteria

The application of parametric criteria will be accompanied by a check of models for applicability (e.g. Kolmogorov-Smirnov test, Shapiro-Wilk test).

The following parametric methods and approaches are supposed to be used:

- To evaluate the differences in continuous variables obtained in one group at two different visits – Student t-test for paired samples.
- 2. To evaluate time changes in parameters compared analysis of variance (ANOVA) or covariance (ANCOVA) modified with repeated measures.
- 3. In case of multiple comparisons of the groups various corrections for multiplicity will be used, e.g. Dunnett, Tukey, Scheffe, Holm adapted test, etc.
- 4. Generalized Linear Models and/or Mixed Linear Models will be used in case of abnormal data distribution.
- 5. Selection of the type of distribution, specification of factor and covariance structures of the model will be made using fit-statistics such as AIC (Akaike information criterion).

The following SAS software programs are supposed to be applied to the above listed tests and techniques:

- UNIVARIATE normality verification of the distributions under comparison
- CORR, MEANS calculation of descriptive statistics
- TTEST Student's test with all modifications
- GLM generalized linear models for studying temporal dynamics (ANOVA, ANCOVA)
- GENMOD generalized linear models

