- MIXED mixed linear models.

Non-parametric criteria

Below are potential types of comparisons with relevant criteria:

- 1. To evaluate time changes in the parameters compared Friedman test, non-parametric analogue of analysis of variance with repeated measures.
- For frequency analysis of contingency tables 2×2 χ2 (if the frequency under comparison > 5) or exact Fisher's test (if one of the frequencies under comparison < 5).

- 3. Cochran-Mantel-Haenszel test (modified χ^2 test for multiple comparisons) to perform frequency analysis based on independent strata.
- 4. For frequency analysis of data on presence/absence of an event or outcome during repeated measurements (contingency tables with dependent strata) survival analysis.

To perform the above-mentioned nonparametric statistical analysis the following SAS procedures are to be used:

- FREQ Friedman test, χ2 test and/or exact Fisher's test; Cochran-Mantel-Haenszel test
- LIFETEST, PHREG survival analysis
- NPAR1WAY Mann-Whitney U-test

Safety parameters

Adverse events recorded during the study will be grouped into frequency tables by severity, seriousness and relationship with the study drug.

Data presentation

Descriptive statistics will be provided for each study continuous / interval variable. Numerical data will be presented by mean, standard deviation, min and max values. Comparisons suggesting statistical conclusion will have the relevant confidence intervals. Outliers will be analyzed individually. The data will be grouped by visits. The categorical variables will be presented as frequency tables by visits.

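### Mixed linear models are triggered by non-normal data rather than by incomplete visits, so a normality test could decide whether NIHSS data from patients who leave after Day 12 are used

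*Combined protocol and SAP*

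**What the plan says.** All references are to the combined protocol and SAP.

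- Secondary endpoint 1 is "Changes in NIHSS score on treatment day 12, 90". In the schedule of study procedures, the row "Filling NIHSS scale" is marked at Visits 1, 2 and 4. MoCA, the primary scale, is marked at Visits 1 and 4 only.
- Parametric criteria, item 2: "To evaluate time changes in parameters compared analysis of variance (ANOVA) or covariance (ANCOVA) modified with repeated measures". The list of SAS programs that follows has "GLM generalized linear models for studying temporal dynamics (ANOVA, ANCOVA". MIXED is a separate entry.
- Parametric criteria, item 4: "Generalized Linear Models and/or Mixed Linear Models will be used in case of abnormal data distribution". Item 5 adds that "specification of factor and covariance structures of the model will be made using fit-statistics such as AIC", with no link to non-normality.
- The opening of Statistical criteria uses parametric methods only while their conditions hold: "parametric to obtain effective estimates for random parameters in case the relevant conditions of method/model applicability are not violated (e.g. sphericity, normality". Everything else goes to nonparametric methods. For those, item 1 reads "To evaluate time changes in the parameters compared Friedman test, non-parametric analogue of analysis of variance with repeated measures".
- The Full Analysis Set leaves out a treated, eligible patient only if there are no data at all after dosing, so a patient seen at Day 12 and then lost stays in. The Per Protocol set takes only patients who completed every visit.
- No section assigns a test to NIHSS, says whether Day 12 and Day 90 are modelled together, or gives a rule for missing values.

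**The concern.** Item 4 is half right. A generalized linear model is a reasonable response to a non-normal outcome. A linear mixed model is not, because its errors are also taken as normal. Its strengths are that it uses every observed visit and allows a flexible covariance over time, and the plan makes neither of these the reason for choosing it.

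NIHSS is the only efficacy scale with two post-baseline assessments, so it is where the choice matters. PROC GLM with a REPEATED statement needs every response and deletes a patient who lacks one. The Full Analysis Set, which the plan uses for its intention-to-treat analysis, would then admit patients whom the listed procedure removes, and a Day 12 NIHSS already collected would go unused. At stake are precision at Day 12 and, under some dropout patterns, bias at both days.

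Non-normal NIHSS data also have two competing routes: mixed models under item 4, or the nonparametric list. A Shapiro-Wilk or Kolmogorov-Smirnov result could therefore settle whether incomplete patients count, although it says nothing about missingness.

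**Working it through.** **The plan's own figure.** The documents give no calculation for NIHSS. The only stated sample size is for MoCA. With a difference of 1.3, SD 3.0, two-sided alpha 0.05, power 80%, looks at 0.15, 0.30 and 1, and the stated boundary families with binding acceptance, the drift is 3.024. Then n per arm = 2 × (3.0 × 3.024 / 1.3)² = 97.4, so 98. Next, 98 / 0.8 = 122.5, so 123 per arm and 246 in total. Both stated figures are reproduced, and nothing below changes them.

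**When a patient is lost.** Three conditions must all hold: NIHSS passes the normality check, both post-baseline visits enter one multivariate GLM, and nothing is imputed. The possible routes compare as follows.

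| Route open under the plan | Day 12 value of a patient lost later | Between-arm contrast at each day |
|---|---|---|
| GLM REPEATED, both visits together | dropped | yes |
| Separate ANCOVA per visit | kept | yes, but not specified |
| MIXED under item 4, if non-normal | kept | yes |
| Friedman, if non-normal | depends on set-up | no; it tests change over visits within patients |

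The nonparametric SAS list also names a Mann-Whitney test. Applied visit by visit it would keep the Day 12 value, but the plan does not tie it to NIHSS.

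**Precision at Day 12.** Let d be the share of patients lost between Day 12 and Day 90. The documents do not give d. Take a comparison with 80% power at 123 per arm.

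- Inflation of the standard error = 1 / √(1 − d)
- Power = Φ[(0.842 + 1.960) × √(1 − d) − 1.960]
- At d = 0.20: 2.802 × 0.894 − 1.960 = 0.546, and Φ(0.546) = 0.707

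| d (assumed) | Patients lost of 246 | SE inflation | Power |
|---|---|---|---|
| 5% | 12.3 | 2.6% | 78% |
| 10% | 24.6 | 5.4% | 76% |
| 15% | 36.9 | 8.5% | 73% |
| 20% | 49.2 | 11.8% | 71% |

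**Why 20% is a ceiling at the planned rate.** The sample-size section counts 246 from signed consent and 196 as completing per protocol. The gap can include screening failures and eligibility errors (withdrawal criteria 1 and 5), who are outside the Full Analysis Set. It can include withdrawals before Day 12. It can also include protocol deviators who have both NIHSS values.

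**Bias.** These are simulations with assumed values: 123 per arm, SD 3, correlation 0.7 between Day 12 and Day 90, about 20% loss, and a true benefit of 1.0 point. The complete-case estimates were:

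| Dropout mechanism (assumed) | Day 12 | Day 90 |
|---|---|---|
| Random | unbiased | unbiased |
| Depends on Day 12 score relative to own arm, same rule in both arms | 1.00 | 1.00–1.01 |
| Depends on Day 12 score itself, same rule in both arms | 0.92 | 0.95 |
| Moderate, score-driven, placebo arm only | 0.46–0.53 | 0.63–0.67 |
| Extreme: all the worst placebo patients leave | −0.06 | 0.25 |

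Another run with one score-driven rule in both arms gave 0.95 for a true 1.07 at Day 12, a ratio of 0.89. In the random, same-rule score-driven and placebo-only scenarios, the likelihood-based estimate, which uses all Day 12 values, stayed at 0.99–1.01. Dropout in these simulations depends on observed Day 12 scores, the setting in which that estimate is valid.

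**The case against.** The strongest reply is that the plan nowhere says these patients are dropped. Its methods are a list of intended tools, and none is tied to NIHSS. NIHSS is a bounded integer score limited to 8–12 at entry, so it may well fail a normality test. Item 4 would then permit MIXED, which keeps the patient. Item 5, on covariance structures, suggests that mixed models were in view anyway. Separate analyses per visit would also keep every Day 12 value.

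Much of this stands, and it rules out three stronger readings that a reader might infer:

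- *That the plan discards Day 12 NIHSS for every later dropout.* This is an inference that needs all three conditions above, and the documents state none of them.
- *That about 49 patients will be lost.* This treats the whole 20% as loss after Day 12. The outpatient stage is 78 of the 90 days, but calendar time does not show when patients leave.
- *That both contrasts are biased whenever dropout relates to early recovery.* With the same rule in both arms the bias is nil or small. It becomes large only when score-driven dropout differs by arm, and the documents give no reason to expect that.

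The reply does not rescue the trigger itself. If failing a normality test is what keeps incomplete patients, the outcome of that test governs the handling of missing visits. The mention of sphericity, which matters only with three or more repeated levels, makes a joint multi-visit analysis a natural reading of item 2. Friedman, the alternative named for time changes, gives no arm contrast at either day.

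**Conclusion.** The concern holds as a misplaced trigger and an unspecified NIHSS analysis. Item 4 offers linear mixed models for a problem that they do not solve, and the listed default for time changes can remove Full Analysis Set patients who have Day 12 but not Day 90.

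The cost is modest at realistic levels of late loss: power at Day 12 of 78% to 76% with 5–10% loss, and 71% at most with the full planned 20%. These figures assume a comparison with 80% power at 123 per arm. The size of any bias rests on assumed SD, correlation and dropout mechanism, and should be quoted only as a range.

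The scope is one secondary endpoint. MoCA has a single post-baseline assessment, so the primary analysis and the sample size are untouched. The per-protocol analysis excludes these patients under any model. The change is worth making because it is cheap, but the trial's main conclusion does not depend on it.

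**What to change.** For NIHSS in the Full Analysis Set, prespecify one PROC MIXED model, a procedure that the plan already lists:

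- Response: NIHSS at Day 12 and Day 90.
- Terms: arm, visit, arm-by-visit and baseline NIHSS, with unstructured covariance.
- Patients: everyone in the set with at least one post-baseline NIHSS.
- Report: the between-arm contrast with its confidence interval at each day.

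In item 4, delete non-normality as the trigger for mixed linear models; it may stay for generalized linear models. State that the NIHSS model does not depend on a normality test.

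The cost is SAP wording and a few lines of SAS code, with no new data or visits. The small downside is that the model relies on missing-at-random, which the SAP should say.
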